#### Rollover Subjects from Trial 331-10-234

*Screening/Baseline:* Subjects will be assessed for eligibility at the last visit of the double-blind trial (ie, Week 6 visit of Trial 331-10-234). Subjects or their parent/legal guardian will complete a separate ICF and subjects will provide assent as required for participation in Trial 331-10-236 before any procedures specific to the open-label trial are performed. The assessments from the last visit of the double-blind trial will serve as the baseline measures for Trial 331-10-236 for any assessment that is not unique to the open-label trial. Medical history will be updated, if necessary.

*Open-label Treatment:* Eligible subjects from Trial 331-10-234 will receive daily treatment with open-label brexpiprazole in the open-label treatment period of Trial 331-10-236 as described in [Section 3.2.1](#).

*Follow-up:* Subjects will be followed up for safety via telephone contact or clinic visit 21 ( $\pm$  2) days after the last dose of IMP.

#### De Novo Subjects

[figure not shown]
*Screening:* Subjects will enter a pretreatment screening phase that will range from a minimum of 3 days to a maximum of 28 days to assess eligibility criteria and to wash out from prohibited concomitant medications, if applicable. Screening begins on the day that the parent/legal guardian signs the ICF and provides assent (subject) as required, based on the local requirements. Subjects will be assigned a unique screening number for each subject with a signed ICF/completed assent prior to enrollment. If a de novo subject previously participated in Trial 331-10-234, they will retain their subject identification number from Trial 331-10-234. Subjects who are able to complete the required washout of prohibited medications per [Table 4.1-1](#) will proceed directly to the baseline (Day 1) visit of the open-label treatment period after completion and review of screening

[figure not shown]
assessments provided that all eligibility criteria are met (ie, laboratory test results, electrocardiograms [ECGs]). If the washout of prohibited medications per [Table 4.1-1](#) is not appropriate for subjects, in the opinion of the investigator, the subjects will participate in the conversion period.

*Conversion:* If the washout of prohibited medications prior to the baseline (Day 1) visit of the open-label treatment period is not appropriate for subjects, in the opinion of the investigator, the subjects will undergo cross-titration to oral brexpiprazole for 1 to 4 weeks, as described in [Section 3.2.2](#). Visits will occur at the end of each week during the conversion period. The goal of de novo subjects during the conversion period is to achieve a brexpiprazole monotherapy target starting dose of 1, 2, or 3 mg daily at any time after Week 1 per the investigator's discretion and to achieve the required washout of prohibited medications as per [Table 4.1-1](#). The subject will proceed to the baseline (Day 1) visit of the open-label treatment period once the target starting dose has been achieved and the required washout of prohibited medications has been completed.

*Baseline and Open-label Treatment:* After completing baseline assessments, eligible subjects will receive daily treatment with open-label brexpiprazole in the open-label treatment period, as described in [Section 3.2.2](#).

*Follow-up:* Subjects will be followed up for safety via telephone contact or clinic visit 21 ( $\pm 2$ ) days after the last dose of IMP.

**Figure 3.1-1 Trial Design Schematic - Rollover Subjects from Trial 331-10-234**

**Figure 3.1-2 Trial Design Schematic - De Novo Subjects**

### **3.2 Trial Treatments**

All doses of open-label IMP are to be taken orally once daily and can be administered without regard to meals. Every effort should be made to administer the open-label IMP at the same time every day. If the titration schedule needs to be adjusted due to clinical or subject-specific need, the site should discuss with the medical monitor.

#### **3.2.1 Rollover Subjects from Trial 331-10-234**

The first dose of open-label brexpiprazole will be taken 1 day after the last dose of double-blind IMP is taken in Trial 331-10-234 so that treatment continues without interruption. Whenever possible, it is anticipated that the last dose of the double-blind, phase 3 efficacy trial will be taken the day of the Week 6 visit of Trial 331-10-234 (ie, the day of the screening/baseline visit for the open-label trial). Subjects should not be dosed with using double-blind (331-10-234) and open-label (331-10-236) study medication on the same day.

Rollover subjects from Trial 331-10-234 will begin dosing with brexpiprazole 0.5 mg/day on Day 1, increasing to 1 mg/day on Day 5, and an optional increase to 2 mg/day if tolerated on Day 8 of the open-label treatment period. If the 2 mg dose is well tolerated, but the response is inadequate, weekly dose increases can be made in 1 mg increments to a maximum of 4 mg/day. Dose changes are allowed based on the clinical judgment of the investigator at scheduled or unscheduled visits according to his/her clinical judgment based on the subject's response to treatment. Daily dosing for this trial includes 1 mg, 2 mg, 3 mg, or 4 mg.

The dose of brexpiprazole may be decreased at any time based on the investigator's judgment after the start of the open-label treatment period. Dose decreases will occur in 1 mg decrements, with the frequency of the 1-mg decreases based upon tolerability. Those unable to tolerate the 1 mg daily dose of brexpiprazole must be withdrawn from the trial. The dosing strategy is summarized in [Table 3.2.1-1](#). Rechallenge with higher doses of brexpiprazole (ie, in 1 mg/day increments) is permitted following dose decreases, if clinically warranted based on the investigator's judgment.

If clinically indicated, subjects may return to the clinic for unscheduled visits if dose adjustments for brexpiprazole are required between scheduled visits. Dose adjustments must ultimately be made based upon the clinical judgment of the investigator as it relates to tolerability and therapeutic response.

| Table 3.2.1-1 Dose Adjustments for Brexpiprazole in the Open-label Treatment Period (Both Rollover Subjects from Trial 331-10-234 and Nonconversion De Novo Subjects) |                            |  |
|--|----------------------------|--|
| Trial Visit   | Dose Options        | Dose Changes  |
| Start of the open-label treatment period, Days 1–4   | 0.5 mg/day (starting dose) | Not applicable   |
| Days 5–7   | 1 mg/day                   | Not applicable   |
| Days 8–14  | 1 or 2 mg/day              | Maintain same dose or option to increase to 2 mg/day if tolerated  |
| Days 15–21   | 1, 2, or 3 mg/day          | Maintain same dose, or option to increase or decrease by 1 mg/day (minimum dose 1 mg/day)                                |
| Day 22 (Week 3) to Month 24  | 1, 2, 3, or 4 mg/day       | Maintain same dose, or option to increase or decrease dose by 1 mg/day (minimum dose 1 mg/day and maximum dose 4 mg/day) |

### **3.2.2 De Novo Subjects**

If the washout of prohibited medications per [Table 4.1-1](#) is not appropriate for de novo subjects, in the opinion of the investigator, the subjects must enter a conversion period to cross-titrate from their current antipsychotic treatment(s) to brexpiprazole monotherapy and to washout from prohibited medications. All other de novo subjects will enter the trial at the baseline (Day 1) visit of the open-label treatment period (see [Section 3.2.2.2](#)) after completion and review of screening assessments, provided that all eligibility criteria are met (ie, laboratory test results, ECGs), and will follow the dosing strategy for rollover subjects ([Table 3.2.1-1](#)).

#### **3.2.2.1 Conversion**

The purpose of the 1- to 4- week conversion period is to cross-titrate de novo subjects from current antipsychotic treatment(s) to monotherapy with brexpiprazole 1, 2, or 3 mg/day and achieve the required washout of prohibited medications per [Table 4.1-1](#) to minimize the possibility of rebound (eg, cholinergic or histaminergic) from abrupt changes in antipsychotic medication. The recommended procedure for initiation of oral brexpiprazole is an ascending cross-titration scheme. The recommended procedure as it pertains to this protocol is summarized in [Table 3.2.2.1-1](#).

**Table 3.2.2.1-1      Recommendation for Switching from Other Antipsychotics to Oral Brexpiprazole Monotherapy**

| Trial Visit                    | Conversion Period a |                 |               |                   |                   | Baseline of Open-label Tx b |
|--------------------------------|--------------------------------|-----------------|---------------|-------------------|-------------------|--|
|                                | Conversion Baseline            | Week 1          | Week 2        | Week 3            |                   |  |
| Dose of brexpiprazole          | 0.5 mg/day                     | 0.5 or 1 mg/day | 1 or 2 mg/day | 1, 2, or 3 mg/day | 1, 2, or 3 mg/day |  |
| Dose of other antipsychotic(s) | No change                      | No change       | Decrease      | Discontinue       | Discontinue       |  |
| Dose of aripiprazole           | Decrease                       | Decrease        | Discontinue   | Discontinue       | Discontinue       |  |

Tx = treatment.

**Note: Washout of required prohibited medications is per [Table 4.1-1](#).**

aConversion period will last for 1 to 4 weeks.

bThe baseline (Day 1) visit of the open-label treatment period will coincide with the end of the conversion period which is up to 4 weeks in duration

The scheme in [Table 3.2.2.1-1](#) represents the optimal approach for conversion of subjects from other antipsychotic(s) to brexpiprazole and is highly recommended for use in this trial; however, the investigator may adjust the dose(s) of other antipsychotic(s) during 1- to 4-week cross-titration as deemed appropriate for individual subjects. The dose of brexpiprazole can increase up to 3 mg/day during cross-titration, but cannot decrease to less than 1 mg/day. Subjects must achieve a minimum monotherapy dose of brexpiprazole 1 mg/day at the end of the conversion period/baseline (Day 1) of the open-label treatment period in order to progress to the open-label treatment period.

### **3.2.2.2      Open-label Treatment Period**

Timing of the first dose of brexpiprazole in the open-label treatment period for de novo subjects will be as follows:

- De novo subjects who participate in the 1- to 4- week conversion period, will receive open-label brexpiprazole in the open-label treatment period once all prohibited medications are discontinued during the conversion period per [Table 4.1-1](#) and once all baseline evaluations are completed.
- De novo subjects who are able to complete the required washout of prohibited medications per [Table 4.1-1](#) will receive the first dose of open-label brexpiprazole in the open-label treatment period as soon as all screening and baseline evaluations are completed.

De novo subjects who participated in the conversion period will begin dosing with brexpiprazole 1, 2, or 3 mg/day in the open-label treatment period. If this dose is well tolerated, but the response is inadequate, weekly dose increases can be made in 1 mg

increments up to a maximum dose of 4 mg/day, based on the clinical judgment of the investigator.

Daily dosing for this trial includes 1, 2, 3, or 4 mg.

The maximum dose of brexpiprazole to be used in this trial is 4 mg daily. The dose of brexpiprazole may be decreased at any time based on the investigator's judgment after the start of the open-label treatment period. Dose decreases will occur in 1 mg decrements, with the frequency of the 1 mg decreases based upon tolerability. Those unable to tolerate the minimum 1 mg daily dose of brexpiprazole must be withdrawn from the trial. The dosing strategy is summarized in [Table 3.2.2.2-1](#). Rechallenge with higher doses of brexpiprazole (in 1 mg/day increments) is permitted following dose decreases, if clinically warranted based on the investigator's judgment.

Dose adjustments must ultimately be made based upon the clinical judgment of the investigator as it relates to tolerability and therapeutic response.

| Table 3.2.2.2-1 Dose Adjustments for Brexpiprazole in the Open-label Treatment Period for De Novo Subjects after Conversion |                      |  |
|--|----------------------|--|
| Trial Visit   | Dose Options  | Dose Changes  |
| Start of the open-label treatment period, Days 1–7   | 1, 2, or 3 mg/day    | Maintain same dose, or option to increase or decrease dose by 1 mg/day (minimum dose 1 mg/day)                           |
| Days 8–14 and Day 15 to Month 24   | 1, 2, 3, or 4 mg/day | Maintain same dose, or option to increase or decrease dose by 1 mg/day (minimum dose 1 mg/day and maximum dose 4 mg/day) |

### 3.3 Trial Population

#### 3.3.1 Number of Subjects and Description of Population

The trial population will include subjects from Trial 331-10-234 and as needed de novo subjects between 13 and 17 years of age, inclusive, at the time of informed consent/assent and at baseline (Day 1) visit of the open-label treatment period. For de novo subjects who did not participate in Trial 331-10-234, the initial diagnosis of schizophrenia for this trial (as defined by DSM-5 criteria) must be made and documented and the diagnosis confirmed by the K-SADS-PL. Subjects from Trial 331-10-234 who turned 18 years old during that trial are also permitted to enroll in this trial. Approximately 350 subjects are anticipated to be enrolled with the expectation that at least 100 will complete 1 year of exposure to open-label brexpiprazole.

### **3.3.2      Subject Selection and Numbering**

At screening, de novo subjects will be assigned a unique subject identification number upon signing the ICF and providing assent based on sequential enrollment in the trial, as required. Subjects from Trial 331-10-234 will retain their subject identification numbers from Trial 331-10-234 and are required to sign a new ICF and assent form for this trial, as required. The clinical site will maintain a list identifying all subjects by their subject identification number and initials.

## **3.4      Eligibility Criteria**

### **3.4.1      Informed Consent**

Informed consent will be freely obtained from all subjects (or their guardian or legally acceptable representative, as applicable for local laws) and documented. The ICF will be approved by the same institutional review board/independent ethics committee (IRB/IEC) that approves this protocol. Subjects who are too young to sign an ICF either via wet signature or electronic signature (e-signature) will provide informed assent per local law, and the subject must be able to understand that he or she can withdraw from the trial at any time and for any reason.

Each ICF will comply with the International Conference on Harmonisation (ICH) Good Clinical Practice (GCP) Guideline and local regulatory requirements. The investigator will ensure that the sponsor reviews and authorizes any site-specific ICF used in the trial before submission to the IRB/IEC.

Investigators may discuss trial availability and the possibility for entry with a potential subject without first obtaining consent. However, informed consent must be obtained and documented before initiation of any procedures that are performed solely for the purpose of determining eligibility for this trial, including withdrawal from current medication(s).

Potential subjects are free to refuse entry into the trial, or withdraw from the trial at any time, without justification, and there will be no consequences to their further care.

At sites where the electronic ICF application is used, prospective trial participants will be provided with controlled access to the application by trial site staff. When the trial site staff and the participant agree that the participant has enough information to make an informed decision to participate, the participant will electronically sign the ICF or assent form in the electronic ICF application and an electronic date and timestamp will be applied to the signature. The subject will be given a printed, signed copy of the ICF and assent form. Any other parties required by the IRB/IEC (trial site staff, witnesses, or

legally acceptable representative) are also required to sign electronically and these signatures will be stored with the electronic ICF in accordance with the ICH GCP Guideline and local regulatory requirements/guidelines. These signatures cannot be altered, removed, or copied. At sites where the electronic ICF application is not used, paper consent and assent forms will be signed after trial site staff and the participant agree that the participant has enough information to make an informed decision to participate. Any other parties required to provide signatures will also sign the paper forms, and the forms will be stored in accordance with the ICH GCP Guideline and local regulatory requirements/guidelines.

Subjects or their parent/legal guardian or legally acceptable representative, as applicable for local laws, may be asked to sign additional ICFs if the protocol is amended, and the changes to the protocol results in additional information that needs to be provided to the subjects, so that they can make a knowledgeable and voluntary decision on trial participation.

If any subject should turn 18 years of age (or the age of adulthood as specified by local laws or regulations) following entry into Trial 331-10-236, the appropriate informed consent must be obtained from the subject. The subject shall be given a copy of the signed ICF and the original shall be kept on file by the investigator.

### **3.4.2        Inclusion Criteria**

#### **3.4.2.1        Rollover Subjects**

Subjects are required to meet the inclusion criteria presented in [Table 3.4.2.1-1](#).

| Table 3.4.2.1-1      Inclusion Criteria for Rollover Subjects from Trial 331-10-234 |   |
|--|---|
| 1.   | Written informed consent/assent obtained from a legally acceptable representative (eg, guardian) or subject prior to the initiation of any protocol-required procedures. In addition, the subject must provide informed assent at screening and must be able to understand that he or she can withdraw from the trial at any time. All informed consent/assent procedures must be in accordance with the trial site's IRB/IEC and local regulatory requirements.  |
| 2.   | Ability, in the opinion of the principal investigator, of the subject and the subject's legally acceptable representative (eg, guardian) or caregiver(s) to understand the nature of the trial and follow protocol requirements, including the prescribed dosage regimens, tablet ingestion, and discontinuation of prohibited concomitant medications, to read and understand the written word in order to complete subject-reported outcomes measures, and to be reliably rated on assessment scales.   |
| 3.   | Male and female subjects 13 to 18 years of age, inclusive, at the time of informed consent/assent and at baseline. Subjects who turned 18 years old during Trial 331-10-234 are permitted in this trial.  |
| 4.   | Subjects who complete Trial 331-10-234 and who, in the opinion of the investigator, could potentially benefit from monotherapy treatment with oral brexpiprazole for schizophrenia. The baseline visit for Trial 331-10-236 coincides with the Week 6 visit of Trial 331-10-234. If the visit cannot be done within $\leq$ 7 days of the Week 6 visit of Trial 331-10-234 then the subject may be able to enter Trial 331-10-236 as a de novo subject following approval by the medical monitor.  |
| 5.   | Outpatient status at the last visit of Trial 331-10-234. Hospitalization for psychosocial reasons (eg, homelessness or need for shelter that is unrelated to the subject's underlying psychiatric condition) will be considered outpatient status for the purpose of enrollment in Trial 331-10-236. Subjects remaining in hospital at the Week 6 visit of Trial 331-10-234 (for other than psychosocial reasons) will be permitted to enroll in Trial 331-10-236 at the Week 6 visit of the double-blind trial if they are planned to be discharged from the hospital before the open-label treatment period Week 1 visit of Trial 331-10-236 and following approval by the medical monitor. |

### 3.4.2.2      De Novo Subjects

Subjects are required to meet the inclusion criteria presented in [Table 3.4.2.2-1](#).

| Table 3.4.2.2-1      Inclusion Criteria for De Novo Subjects |   |
|---|---|
| 1.  | Written informed consent obtained from a legally acceptable representative (eg, guardian) prior to the initiation of any protocol-required procedures. In addition, the subject must provide informed assent at screening and must be able to understand that he or she can withdraw from the trial at any time. All informed consent/assent procedures must be in accordance with the trial site's IRB/IEC and local regulatory requirements.  |
| 2.  | Ability, in the opinion of the principal investigator, of the subject and the subject's legally acceptable representative (eg, guardian) or caregiver(s) to understand the nature of the trial and follow protocol requirements, including the prescribed dosage regimens, tablet ingestion, and discontinuation of prohibited concomitant medications, to read and understand the written word in order to complete subject-reported outcomes measures, and to be reliably rated on assessment scales. |
| 3.  | Male and female subjects 13 to 17 years of age, inclusive, at the time of informed consent/assent and at the baseline (Day 1) visit of the open-label treatment period. Subjects who turned 18 years of age since participation in Trial 331-10-234, if applicable, are permitted to enroll in this trial.  |

| Table 3.4.2.2-1 Inclusion Criteria for De Novo Subjects                         |  |
|--|--|
| 4.   | Subjects with a current primary diagnosis of schizophrenia, as defined by DSM-5 criteria and a history of the illness (diagnosis or symptoms) for at least 6 months prior to screening (as per subject, family, or healthcare provider, or by previous medical records). For subjects who did not participate in Trial 331-10-234, the initial diagnosis of schizophrenia for this trial (as defined by DSM-5 criteria) must be made and documented by an adequately trained clinician (psychiatrist, or local medical equivalent who is experienced in treating adolescents with schizophrenia), and the diagnosis should then be confirmed utilizing the K-SADS-PL performed by an adequately trained rater at the time of entry into Trial 331-10-236. (Subjects with a diagnosis of ADHD and treated with stimulants or other ADHD medications within 28 days are prohibited.) |
| 5.   | Subjects who, in the investigator's judgment, require treatment with antipsychotic medication(s).  |
| 6.   | Removed with Amendment 2.  |
| 7.   | Outpatient status. Hospitalization for psychosocial reasons (eg, homelessness or need for shelter that is unrelated to the subject's underlying psychiatric condition) will be considered outpatient status for the purpose of enrollment in Trial 331-10-236. Subjects hospitalized at the time of the Trial 331-10-236 screening visit will be permitted to be screened for the trial if they are planned to be discharged from the hospital prior to the baseline (Day 1) visit of the open-label treatment period and following approval by the medical monitor.   |
| 8.   | Subjects willing to discontinue all prohibited psychotropic medications to meet protocol-required washouts prior to and during the trial period.   |
| Inclusion Criteria Assessed Prior to Entry into the Conversion Period           |  |
| 9.   | Removed with Amendment 4.  |
| 10.  | Subject is receiving antipsychotic(s) other than clozapine. These subjects must be cross-titrated to brexpiprazole monotherapy over 1 to 4 weeks during the conversion period to a minimum dose of 1 mg/day as a starting dose in the open-label treatment period (see Section 3.2.2.1 ).  |
| Inclusion Criteria Assessed Prior to Entry into the Open-label Treatment Period |  |
| 11.  | Adequate washout of prohibited concomitant medications (see Table 4.1-1 ).   |
| 12.  | Subject is ready to receive oral brexpiprazole as monotherapy for treatment of schizophrenia.  |

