For rollover subjects, Trial 331-10-236 will consist of a 24-month open-label treatment period and a 21 ( $\pm$  2) day follow-up period. For de novo subjects, Trial 331-10-236 will consist of a 3- to 28-day screening phase, a 1 to 4 weeks conversion phase (if necessary), a 24-month open-label treatment phase, and a 21 ( $\pm$  2) day follow-up period. Visit windows of  $\pm$  3 days will be permitted during the trial; however, every effort will be made to ensure the individual open-label treatment period does not exceed 24 months.

The decision to enroll into this open-label trial from Trial 331-10-234 will be a joint decision between the investigator and subject/parent/guardian or legally acceptable representative, as applicable for local laws and will be made without knowledge of the subject's double-blind treatment assignment. The availability of the open-label trial should be discussed with these subjects and an informed consent/assent specific to Trial 331-10-236 must be completed for the Trial 331-10-234 rollover subjects before any trial-related procedures can take place. For rollover subjects, the informed consent form (ICF) for the open-label trial may be provided to potential candidates or their parent/legal guardian or legally acceptable representative, as applicable for local laws, for review and discussion toward completion of the double-blind trial, but the form must not

be signed until the day of the screening/baseline visit for Trial 331-10-236 (ie, the Week 6 visit of Trial 331-10-234). For de novo subjects, screening begins on the day that the subject or their parent/legal guardian or legally acceptable representative, as applicable for local laws, signs the ICF. If any subject should turn 18 years of age (or the age of adulthood as specified by local laws or regulations) following entry into Trial 331-10-236, the appropriate informed consent must be obtained from the subject.

A schematic of the trial design is provided in [Figure 3.1-1](#) (rollover subjects) and [Figure 3.1-2](#) (de novo subjects).

The trial will be organized as follows:

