Subjects excluded for positive drug/alcohol screen are not eligible to be rescreened for participation in the trial. However, de novo subjects excluded for other reasons may be rescreened at any time if the exclusion characteristic has changed. In the event that the subject is rescreened, a new ICF and assent must be signed and a new screening number assigned. If a de novo subject previously participated in Trial 331-10-234, they will retain their subject identification number from Trial 331-10-234.

Subjects who are discontinued from the trial during the conversion period are not eligible to be rescreened.

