## **4 Restrictions**

### **4.1 Prohibited Medications**

All subjects must agree to abstain from prohibited medications during the trial. Prohibited medications for de novo subjects are listed in [Table 4.1-1](#). Other therapies prohibited prior to enrollment and during the trial are presented in [Section 4.2](#).

| Table 4.1-1 Washout of Prohibited Medications Required Before the Trial - De Novo Subjects  |   |
|--|---|
| Medication  | Required Washout Prior to Open-label Treatment Period  |
| Antipsychotics
Oral aripiprazole
Oral antipsychotics (other than cariprazine and clozapine)
Depot or long-acting injectable antipsychotics
Cariprazine (Vraylar) and clozapine | 14 days
7 days
5 × half-lives of the medication
6 months                                     |
| Antidepressants
Fluoxetine or Symbax
MAOIs
Citalopram and escitalopram
Venlafaxine and desvenlafaxine
All other antidepressants   | 28 days a
14 days
8 days
3 days
14 days  |
| Atomoxetine
Stimulants  | 28 days with the diagnosis of ADHD;
minimum 5× half-life for subjects
without diagnosis of ADHD |
| Mood stabilizers (ie, lithium or anticonvulsants)  | 7 days  |
| Varenicline  | 5 days  |
| Oral benzodiazepines used as rescue therapy during washout b
Lorazepam, oxazepam, diazepam, or clonazepam
Other benzodiazepines   | 12 hours before scales c
14 days  |
| CYP2D6 inhibitors and CYP3A4 inhibitors and inducers
(see Table 4.1-4 )   | 14 days   |

MAOIs = monoamine oxidase inhibitors.

aExtension to the screening window is needed for washout, contact the medical director.

bUse of IM benzodiazepines and continual use of oral benzodiazepines are prohibited throughout the trial. However, limited use of specific oral benzodiazepines is permitted during screening to treat agitation or insomnia (see [Table 4.1-3](#)).

cBenzodiazepines must not be administered within 12 hours prior to scheduled efficacy and safety assessments, including EPS scales. Investigators are encouraged to delay scale administration until 12 hours have elapsed, if at all possible. However, if delaying administration of efficacy and safety scales is not feasible, the scales should still be administered and the use of benzodiazepine documented, including a notation of the drug name, dose, and time of administration on the eSource.

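### Inclusion criterion 10 sends subjects on cariprazine into a 1- to 4-week conversion, while Table 4.1-1 requires a 6-month cariprazine washout before open-label Day 1; the two must be reconciled.

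*Protocol*

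**What the plan says.** Protocol Table 3.4.2.2-1 groups the later de novo inclusion criteria by when they are assessed. Criterion 10 is in the group checked before conversion: "Subject is receiving antipsychotic(s) other than clozapine. These subjects must be cross-titrated to brexpiprazole monotherapy over 1 to 4 weeks".

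Table 4.1-1 (Section 4.1) lists the washouts under the column title "Required Washout Prior to Open-label Treatment Period". Oral aripiprazole has 14 days, other oral antipsychotics 7 days, and depots five half-lives. "Cariprazine (Vraylar) and clozapine" form one entry at 6 months, and the 7-day entry leaves out both drugs by name.

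Criterion 11, in the group checked before the open-label period, requires "Adequate washout of prohibited concomitant medications" and points to Table 4.1-1. Sections 3.1 and 3.7.1.1.2.2 agree: a subject moves from conversion to Day 1 only when the target starting dose has been reached and the washout is complete.

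On timing, a footnote to Table 3.2.2.1-1 states: "Conversion period will last for 1 to 4 weeks". Brexpiprazole is dispensed at the conversion baseline visit (Section 3.7.1.1.2.2), and Section 3.9 counts treatment as started with the first conversion dose. The text after Table 3.4.3.2-1 adds: "Subjects who are discontinued from the trial during the conversion period are not eligible to be rescreened".

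**The concern.** The protocol treats cariprazine and clozapine alike on leaving conversion but differently on entering it. A site that works through the criteria in order finds that a current cariprazine user meets criterion 10, which says such subjects must be cross-titrated. The 6-month requirement then applies at Day 1 and cannot be met.

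At stake is an adolescent whose antipsychotic is switched and who receives brexpiprazole with no compliant route into the open-label period and no second screening. In the SAP's terms (Section 5), that subject would sit in the conversion-period samples only and add nothing to the target of at least 100 subjects with 12 months of exposure.

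**Working it through.** The plan states no figure for this point, so the check is a comparison of time available with time required.

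**Inputs**
- Conversion: up to 4 weeks = 28 days, with a ±3-day visit window, so at most 28 + 3 = 31 (Table 3.2.2.1-1 footnote; Table 3.7-2 footnote).
- Screening: 3 to 28 days (Section 3.1). The medical monitor may approve an extension, and no upper limit is given (Section 3.7.1.1.2.1).
- Washout: 6 months, counted back from the start of the open-label period (Table 4.1-1).
- Length of 6 months: 6 × 28 = 168 days (the 4-week scheduling month that SAP Section 10.2 says applied before Amendment 5); 365.25 / 2 = 182.6 days (calendar); 6 × 31 = 186 days (the current scheduling month, protocol Section 3.7).

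**Does the switching scheme fit the other washouts?** Table 3.2.2.1-1 discontinues aripiprazole at Week 2 and other antipsychotics at Week 3. With a Week 4 baseline this leaves 28 − 14 = 14 days and 28 − 21 = 7 days, exactly the aripiprazole and other-oral entries of Table 4.1-1. The scheme fits those two entries. Cariprazine can only fall under its line for other antipsychotics.

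**Shortfall = required days − drug-free days before Day 1**

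| When cariprazine is stopped | Drug-free days | vs 168 | vs 182.6 | vs 186 |
|---|---|---|---|---|
| Conversion Week 3 (Table 3.2.2.1-1) | 7 | 161 | 175.6 | 179 |
| Conversion Day 1, 4 weeks | 28 | 140 | 154.6 | 158 |
| Conversion Day 1, 4 weeks + 3 days | 31 | 137 | 151.6 | 155 |
| First day of a full screening, then full conversion | 28 + 28 = 56 | 112 | 126.6 | 130 |
| The same, + 3 days | 59 | 109 | 123.6 | 127 |

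The first three rows describe the person in criterion 10, who is still receiving the drug at conversion entry. At best that person reaches 28/186 = 15% to 31/168 = 18% of the requirement.

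The last two rows describe someone who stops at consent. That person would need screening extended by about 109 to 130 days, roughly four months, and would no longer be receiving cariprazine at conversion entry, so criterion 10 would no longer apply on account of that drug.

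**Rescreening.** Section 3.9 allows rescreening of subjects who fail during screening, and defines screen failures as subjects not started on brexpiprazole. A subject dosed in conversion is outside that allowance and comes under the bar that follows Table 3.4.3.2-1.

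**The case against.** The strongest reply is that the protocol already has ways to stop this subject before any brexpiprazole is given. Section 3.4.3.2 excludes anyone who meets any exclusion criterion, so meeting criterion 10 does not override the rest. Exclusion 19 removes subjects who, in the investigator's judgment, cannot comply with the psychotropic washout; on the arithmetic above, a current cariprazine user fits. Criterion 8 asks for willingness to meet the required washouts. Section 3.7.1.1.2.1 has all criteria reviewed at screening and cites Table 4.1-1, so the site should see the 6-month entry early.

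Much of this stands. A reader might infer that every cariprazine user will be switched to brexpiprazole and then lost. The documents do not support that: these provisions can prevent it, and the medical monitor can extend screening without a stated limit. But exclusion 19 depends on judgment, criterion 8 concerns willingness rather than feasibility, and neither names cariprazine, while criterion 10 says must. They make exposure uncertain; they do not remove the contradiction.

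A reader might also extend the argument to depot antipsychotics. That does not hold. Their washout runs from the last injection, which may be well before consent; the documents give no half-lives; and exclusion 30 already covers depots.

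Nor do the documents say that the antipsychotic being stopped was working, or that the switch would destabilise the subject.

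**Conclusion.** The contradiction holds on the wording of the two tables. For a subject still on cariprazine at conversion entry, the 6-month washout is missed by 137 to 158 days if the drug is stopped on conversion Day 1, and by 161 to 179 days under the recommended scheme. No reading of a month changes this. It assumes that conversion stays within its 4 weeks plus window; the extension provision concerns screening only.

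The consequence is conditional: such a subject could be given brexpiprazole without being able to reach Day 1 or be rescreened, if criterion 10 is applied as written and exclusion 19 is not invoked. The number affected is not stated. It is probably small, because de novo subjects come from select sites and SAP Section 8.1.2 expects few in conversion. No endpoint or planned analysis is shown to be affected. The point should be corrected because of that possible exposure, not because it threatens the trial's results. Which washout is clinically right is not judged here.

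**What to change.** Reconcile criterion 10 of Table 3.4.2.2-1, together with Section 3.2.2.1 and Table 3.2.2.1-1, with the cariprazine/clozapine entry of Table 4.1-1, so that the criteria applied before conversion and those applied at Day 1 agree for the same drug. The sponsor decides which rule stands.

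The cost is about one line in each affected place, by protocol amendment or clarification letter. The sample size, the SAP and the planned analyses need no change.
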